## 9. Responsibilities

### 9.1. Good Clinical Practice

**9.1.1.** The rights and welfare of the individual clinical research subject must always be the paramount consideration in conducting clinical research. Accordingly, clinical research must be conducted in a manner that protects the rights, welfare and confidentiality of the human subject and also assures data credibility by protecting the integrity of accurate data that has been demonstrably collected according to the approved protocol.

### 9.2. Investigator Responsibilities

**9.2.1.** The Investigator is responsible for:

- 9.2.1.1. Ensuring that the study is conducted according to the signed investigator statement/agreement, the investigational plan (study protocol), applicable regulations
- 9.2.1.2. Ensuring that all persons assisting with the trial are adequately informed about the protocol, the study drug, their trial-related duties and functions
- 9.2.1.3. Protection of the rights, safety, and welfare of subjects under the investigator's care
- 9.2.1.4. Control of the study drug included in the investigation.
- 9.2.1.5. Assuring that each subject's informed consent is obtained appropriately
- 9.2.1.6. Proper delegation of authority for the conduct of various aspects of the study so that the investigator retains control and knowledge of the study

### 9.3. Control of Study Drug

**9.3.1.** The investigator shall control the study drug. The Investigator is responsible to ensure that:

- 9.3.1.1. The study drug is administered only to subjects under the investigator's personal supervision or under the supervision of a qualified sub-investigator responsible to the investigator.
- 9.3.1.2. The study drug is not to be supplied/provided to any person not authorized to receive it.
- 9.3.1.3. Adequate records of the disposition of the study drug are maintained, including dates, quantity, receipt, distribution to subjects, and disposition.

### 9.4. Medical Decision Making

**9.4.1.** Primary Investigator or sub-investigator must be designated as responsible for all trial-related medical decisions. Medical decisions must be made by a qualified person permitted by state licensure laws to make or enact such decisions. The investigator should:

- 9.4.2.** Ensure that adequate medical care is provided to a subject for any adverse events related to the trial, during and as follow-up to a subject's participation.
- 9.4.3.** Inform a subject when medical care is needed for intercurrent illness (es) of which the investigator/sub-investigator becomes aware.
- 9.4.4.** Inform the subject's primary physician about the subject's participation in the trial if the subject agrees to the primary physician being informed, and has signed a HIPAA Authorization form permitting such disclosure.

### 9.5. IRB/IEC Review and Approval

**9.5.1.** The investigator shall assure that initial and continuing review of the proposed clinical study is performed according to the policies and procedures of the Central Institutional Review Board (IRB), as well as with any other IRB that has jurisdiction.

**9.5.2.** Continuous approval from the IRB must be maintained.

**9.5.3.** All unanticipated problems involving risk to human subjects or others are promptly reported to the IRB. All serious adverse events are reported to the IRB within twenty-four hours of time investigator is aware of the event.

**9.5.4.** Any changes in the research activity are promptly reported to the IRB.

**9.5.5.** No changes are made in the research without IRB approval, except where necessary to eliminate apparent immediate hazards to human subjects.

### 9.6. Informed Consent

**9.6.1.** The Investigator is responsible for obtaining written informed consent from each individual participating in this study after adequate explanation of the aims, methods, objectives, and potential hazards of the study and before undertaking any study related procedures. The investigator must use the most current IRB/IEC-approved consent form for documenting written informed consent. Each informed consent (or assent as applicable) will be appropriately signed and dated by the subject's legally authorized representative and the person conducting the consent discussion, and also by an impartial witness if required by IRB/IEC or local requirements. The consent form will inform subjects about sample retention.

#### **9.7. Confidentiality**

**9.7.1.** The investigator will assure that subjects' anonymity will be strictly maintained and that their identities are protected from unauthorized parties. All information and data will be collected by the investigator. All collected data concerning participants or their participation in this study will be considered confidential and maintained in a HIPAA-compliant electronic medical recording system. Subject data pertinent to the study will be de-identified and access limited only to personnel directly involved in this research study. All data used in the analysis and reporting of this evaluation will be used in a manner without identifiable reference to the participant. Study data will not be transmitted nor disclosed to a third-party. Paper records will be kept in secure files and electronic records will be password protected.

#### **9.8. Study Files and Retention of Records**

- 9.8.1.** The investigator shall keep and maintain adequate and accurate records, including:
- 9.8.2.** Case histories on each individual study subject that record all observations and other data pertinent to the investigation
- 9.8.3.** Screening, enrollment, and informed consent documentation; demonstrating that informed consent was obtained prior to participation in the study
- 9.8.4.** Study reports, including reports of progress, safety, financial disclosure and final completion

#### **9.9. Records retention**

- 9.9.1.** Midland Research Group Inc. will use on-site facility and if storage becomes unavailable due to capacity of documents, then Midland Research Group Inc will use an offsite facility.
- 9.9.2.** FDA regulation requires an investigator to retain records a minimum of two years after the close of the study or after the records are no longer required to support a drug or marketing application, whichever is longer.
- 9.9.3.** Contract commitments must be met.
- 9.9.4.** Record transfer or record destruction should be verified and documented.

#### **9.10. Case Report Forms**

- 9.10.1.** For each subject consented, a study file will be completed by an authorized study staff member who has completed training for this function. The study file will only capture the data required per the protocol schedule of events and procedures. The Inclusion/Exclusion Criteria and Enrollment should be completed only after all data related to eligibility have been received. Subsequent to data entry, a second staff member will perform source data verification.

#### **9.11. Study Drug Accountability and Return**

- 9.11.1.** Unused study drug supplies will be destroyed. Investigator will assist with disposal procedures and provide appropriate instruction for destruction of unused study drug supplies.

#### **9.12. Protocol Compliance**

- 9.12.1.** The Investigator is responsible for ensuring the study is conducted in accordance with the procedures and evaluations described in this protocol.

#### **9.13. Sponsor Responsibilities**

#### **9.14. Protocol Modifications**

- 9.14.1.** Protocol modifications, except those intended to reduce immediate risk to study subjects, may be made only by the Investigator, who must submit all protocol modifications to the IRB in accordance with local requirements and receive documented IRB approval before modifications can be implemented.

**9.15. Study Report and Publications**

**9.15.1.** The Investigator is responsible for submitting any reports within time periods and according to procedures called for by:

9.15.1.1. Midland Research Group Inc . or applicable division or departmental policy or procedures, including the Institutional Review Board (IRB)

9.15.1.2. Contractual agreements with collaborators, etc.

**9.16. Payment Reporting**

**9.16.1.** Investigators and their study staff may be asked to provide services performed under this protocol.

If required under applicable statutory and regulatory requirements, Midland Research Group Inc. will capture and disclose to Federal and State agencies any expenses paid or reimbursed for such services, including any clinical trial payments, meal, travel expenses or reimbursements, consulting fees, and any other transfer of value.

**9.17. Access to Information for Monitoring, Auditing or Inspection**

**9.17.1.** As per contract

**9.18. Study Discontinuation**

**9.18.1.** The investigator reserves the right to terminate the study at any time. Should this be necessary, they will arrange discontinuation procedures and notify the appropriate regulatory authorities and the IRB. In terminating the study, the Investigator will assure that adequate consideration is given to the protection of the subjects' interests.

**9.19. PUBLICATIONS**

**9.19.1.** As per contract

## APPENDIX 1: Midland ART Adherence Survey (MAAS)

**Midland ART Adherence Survey**

Survey # \_\_\_\_\_

Age:  18-35  36-49  50-65  66-99      Ethnicity: \_\_\_\_\_      Gender: \_\_\_\_\_How long on ART?  <1 year       1-5 years       6-10 years       11-15 years       16 or more years

1. Do you sometimes forget to take your HIV medications?	 Yes  No	Current prescribed HIV regimen:
3. Have you ever not taken your meds because you felt worse when you took it?	 Yes  No	 Biktarvy  Genvoya  Julica  Triumeq  Isentress/Isentress HD  Stribild  Dulera  Tivicay  Syntuza  Atripla  Complera  Odefsey  Reyataz or Evotaz  Prezista or Prezcobix
4. When you travel or leave home, do you sometimes forget to bring along your medications?	 Yes  No	 Descovy  Truvada  Epzicom  Edurant  Intelence  Sustiva  Selzentry
5. Did you take your HIV medicine yesterday?	 Yes  No	
6. When you feel like your health is good, do you sometimes stop taking your medicine?	 Yes  No	
7. Do you ever miss doses of your medications because of side effects from them? If so, what side effects?	 Yes  No	

8. How often do you take your HIV medications?

- ALWAYS –never miss a dose
- ALMOST ALWAYS-miss 1-2 times a month
- USUALLY-miss 3- 5 times a month
- SOMETIMES-miss more than 5 times, but take more than 5 times a month
- RARELY-take 3- 5 times a month
- ALMOST NEVER-take 1-2 times a month
- NEVER-do not take the medication

9. How many days in the last week did you not take your HIV medication? \_\_\_\_\_

10. How many days in the last month did you not take your HIV medication? \_\_\_\_\_

11. What is your biggest issue with being able to take your medication: \_\_\_\_\_

We are looking at some ways to help our patients with their medications. Would it be ok to share your responses with your provider if we think we might have some options for you?       Yes       No

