### 6.2.3. Eligibility Criteria

#### 6.2.3.1. Inclusion Criteria

6.2.3.1.1. Meets inclusion criteria of part I of study

6.2.3.1.1.1. Currently on an integrase containing regimen AND

6.2.3.1.1.2. Reports non-adherent due to medication intolerance, defined by pre-determined criteria from Adherence Survey: [indicate a side effect to question 11 OR "yes" to questions 3 OR 7] AND [indicate missing more than 2 doses per month on question 8 OR 9 OR 10]

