##### 6.2.4.2. Positive Screen

6.2.4.2.1. Subjects who screen positive from adherence survey defined as: (1) (indicate "yes" to questions 3 OR 7; or indicate a side effect to question 11) AND (2) (indicate missing more than 2 doses per month on question 8 OR 9 OR 10) will be offered enrollment in Part II.

Table 6.2.4.2.1 Positive Screen for Part 2

Positive screen for Part II one positive response in both columns:	
One from below	One from below
Question 3 = "Yes"	Question 8 = not "always" or "almost always"
Question 7 = "Yes"	Question 9 = greater than 2
Question 11 = "Side effect(s)" or named side effect	Question 10 = greater than 2

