**6.2.4.5. Week 4 Visit**

- 6.2.4.5.1. At 4 week visit, vitals will be taken, pill count will be performed, MAAS and HIV-SI surveys completed. Followed by history, symptom based physical, and laboratory exam. Patient will be given 90-day supply of study drug.

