**6.2.4.7. Week 16 Visit**

- 6.2.4.7.1. At 16 week visit, subjects will have vitals taken, pill count will be performed; both the MAAS and HIV-SI will be completed, followed by history, symptom based physical, and laboratory exam. Pill count will be taken from bottle dispensed at baseline visit. Staff will confirm with patient that they have the commercial medication .

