**6.2.4.8. Early Discontinuation Visit**

- 6.2.4.8.1. If the subject discontinues the study drug prior to the Week 16 Visit, the subject will be asked to return to the clinic within 10 days of stopping study drug for the Early Study Drug Discontinuation Visit. Every attempt should be made to keep the subject in the study and continue to perform the required follow ups and procedures through to the Week 16 Visit. If this is not acceptable to the subject or investigator, the subject may be withdrawn from the study. In the event that the subject is not kept in the study, physical and laboratory exam, as well as the MAAS and HIV-SI should be performed unless the subject does not consent to them.

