**8.5. Part 1 –****8.5.1. Analysis of Primary End-Point**

8.5.1.1. The dependent variable is measured on an ordinal scale (Midland ART Adherence Survey). However, employing Rasch analysis we will convert the data to a standardized range from 0 to 100, where 100 is perfect adherence and zero (0) is complete failure to adhere. Using this scale we will examine the proportion of subjects who meet or exceed 90% adherence.

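### MAAS question 3 has no recall window yet selects subjects into Part 2 and, if scored, carries their pre-switch history into the Week 16 endpoint

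*Protocol*

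**What the plan says.** Appendix 1 words question 3 as "Have you ever not taken your meds because you felt worse when you took it" and gives it no period. Questions 5, 9 and 10 refer to yesterday, the last week and the last month, and the HIV-SI in Appendix 2 covers four weeks.

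The answer is used for selection. Section 6.2.3.1.1.2 requires the subject to "indicate a side effect to question 11 OR 'yes' to questions 3 OR 7", together with a missed-dose criterion. Section 6.2.4.2 repeats the rule: "indicate 'yes' to questions 3 OR 7; or indicate a side effect to question 11".

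The same form is then used for follow-up. Section 6.2.4.5 (Week 4) has "MAAS and HIV-SI surveys completed", section 6.2.4.7 (Week 16) has "both the MAAS and HIV-SI will be completed", and section 6.2.4.8 (early discontinuation) has "as well as the MAAS and HIV-SI should be performed". No section changes the wording of any item after baseline.

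On scoring, section 8.5.1 says "The dependent variable is measured on an ordinal scale (Midland ART Adherence Survey" and "employing Rasch analysis we will convert the data to a standardized range from 0 to 100", with 100 meaning perfect adherence. Sections 8.2.2.1 and 8.6.1 apply the Rasch score to the Part 2 primary endpoint, with optimal adherence set at 90 or more and a hypothesised minimum of 85% optimal. No section lists the scored items or excludes one.

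**The concern.** A truthful yes to a question about whether something has ever happened stays yes. The form's top band for time on ART is 16 years or more, while exposure to study drug is 16 weeks. A subject who once skipped doses because the old regimen made them feel worse must, on a literal reading, give the same answer at Week 16 even after taking every tablet of study drug.

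The trial therefore selects partly on this answer and may then count it against the same subject in the only endpoint it tests. An item that the switch cannot alter says nothing about response to the switch. What is at stake is a real improvement being partly hidden in a study with a target of 30 subjects.

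**Working it through.** **The plan's own figure.** The protocol gives no attainable score, so there is none to reproduce. Its sample size formula (section 8.8.2) gives ln(0.05)/ln(0.90) = 28.43, rounded up to 29 against the stated 30. This point does not affect it.

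**Inputs from the protocol.** Yes/no items: questions 1 and 3 to 7, six in the text available. Question 8 has seven ordered categories, so 6 points. Question 9 runs 0 to 7 days and question 10 is days in the last month. The cut-off is 90. Section 8.5.2.1 asks for category thresholds 1.4 to 5 logits apart.

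**Assumptions.** Which items are scored, how questions 9 and 10 are coded, and the item difficulties.

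**Model.** In a partial-credit Rasch model the raw total r fixes the measure θ(r), the value at which the expected total equals r. With maximum M, and the extreme totals moved inward by e, the score is

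100 × [θ(r) − θ(e)] / [θ(M − e) − θ(e)].

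Question 3 fixed at yes costs one point, so the best attainable total is M − 1 and 100 is out of reach.

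**Hand check of the mechanism.** For six equally difficult yes/no items alone, θ(r) = ln[r/(6 − r)]. With e = 0.3: θ(5) = ln 5 = 1.609 and θ(5.7) = ln(5.7/0.3) = 2.944, giving 100 × (1.609 + 2.944)/(2 × 2.944) = 77.3. With e = 0.5: θ(5.5) = ln 11 = 2.398, giving 100 × (1.609 + 2.398)/(2 × 2.398) = 83.6. This is an illustration only, because the form also carries questions 8 to 10.

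**Grid.** Threshold spacing 1.4, 2, 3, 4 or 5 logits; SD of yes/no difficulty 0, 1 or 2; e = 0.25, 0.3 or 0.5. That makes 5 × 3 × 3 = 45 settings per item set. Best score with question 3 at yes and every other answer perfect:

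| Scored with the six yes/no items | M | Best score | Settings below 90 |
|---|---|---|---|
| Question 8 | 12 | 83.2 to 91.2 | 41 or 42 of 45 |
| Question 8; questions 9 and 10 in five bands each | 20 | 85.7 to 92.7 | 30 of 45 |
| Question 8; question 9 in days | 19 | 86.8 to 95.3 | 12 of 45 |
| Question 8; question 9 in days; question 10 as 0 to 30 days | 49 | 95.7 to 98.3 | 0 of 45 |

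The count in the first row depends on how the yes/no difficulties are spaced. A seventh yes/no item would move these limits by at most 0.3 points.

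**Day counts with one missed day.** Take a subject who answers almost always on question 8 and 1 on question 10. With question 3 scored, the subject is three points below perfect: 89.0 to 91.4, below 90 in 9 of 45 settings. Without it, two points below: 92.2 to 94.8, below 90 in none.

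**Direction.** Fixing one item at its lower category can only lower a subject's score. The proportion at or above 90 therefore falls or stays the same in every setting.

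**The case against.** The strongest objection is that item selection belongs in a statistical analysis plan, which is not shown. Some selection is unavoidable, since the form also holds demographics, a regimen checklist and free text. That is fair as to the list of items. But the wording of question 3 and its reuse after selection are fixed in the protocol, and a plan followed as written would score it.

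Second, some subjects may take the question to mean the current regimen, which at Week 16 is study drug. This stands as a limit. For those subjects the answer can change, and the item then means different things to different people.

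Third, any single lost point has the same numerical effect. With question 3 removed (five yes/no items plus question 8), one other lost point still gives 82.9 to about 91, below 90 in 42 of 45 settings. In short item sets, removal therefore helps mainly subjects who are perfect elsewhere. This stands. The difference is that other lost points can reflect behaviour on study drug, whereas this one records the past. Question 7 is also undated, but it is in the present tense and can change.

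Fourth, the grid has limited authority. The spacing rule in section 8.5.2.1 concerns rating categories and does not govern yes/no items. For question 10 as 0 to 30 days it would imply at least 29 × 1.4 = 40.6 logits between the first and last of 30 thresholds, and the rule of 10 observations per category would need 31 × 10 = 310 responses. This also stands: the grid shows a range and does not predict a value.

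A reader might go further and infer that the 85% target is out of reach, since five subjects unable to reach 90 would cap the result at 25/30 = 83.3%. The protocol does not support that. It needs a best score below 90, which depends on unstated coding, and a number of yes entrants that is not given. Nor does a yes at entry by itself place a subject below 90.

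**Conclusion.** The point holds conditionally. If question 3 is scored and read literally, subjects who entered with a yes carry pre-switch history into the Week 16 score, and the proportion at or above 90 is biased downward or not at all. The error runs against the study's own hypothesis: it can hide a benefit but cannot create one.

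The size is undetermined. It rests on the scored items, their coding and calibration, and the share of yes entrants, none of which the protocol states. Subjects who entered through question 7 or 11 with a no on question 3 are unaffected. The change-from-baseline wording in section 4.2.1.1 is less affected, because the same point is lost at both visits. This should be corrected, because the remedy is small and a decision taken after scoring would look data-driven.

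**What to change.** Keep the present wording of question 3 for screening. Before any Week 16 data are scored, including for the interim analysis in section 6.2.4.1.3, choose one of two options for the Part 2 outcome:

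- **(a) Add a recall window.** Ask question 3 at follow-up over a stated period, such as since the last visit or the last month as in question 10, and ask it over the same window at baseline for comparison. A last-month window has equal length at each visit. Since the last visit would cover about 4 weeks at Week 4 and 16 − 4 = 12 weeks at Week 16. The cost is a small wording change to the form, and a Part 1 calibration of the undated item would not carry over to the dated one.
- **(b) Screening only.** State in sections 8.2.2.1 and 8.6.1 that question 3 is left out of the Part 2 Rasch score at every visit. An otherwise perfect subject can then reach 100. The cost is the loss of one of the two yes/no items on side-effect non-adherence (question 7 remains), and Part 1 must also be scored without question 3 if the two parts are compared.

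Either option is a protocol modification that needs IRB approval under section 9.14. Neither adds a visit.

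### Appendix 1 (MAAS): five of the ten printed items, including all three side-effect routes into Part 2, are not limited to HIV medication, while the other five are

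*Protocol*

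**What the plan says.** Appendix 1 prints ten items, numbered 1 and 3 to 11. Five name HIV medication, such as question 10: "How many days in the last month did you not take your HIV medication". Five do not:

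- question 3: "Have you ever not taken your meds because you felt worse when you took it"
- question 4: "When you travel or leave home, do you sometimes forget to bring along your medications"
- question 6: "When you feel like your health is good, do you sometimes stop taking your medicine"
- question 7: "Do you ever miss doses of your medications because of side effects from them"
- question 11 (open text): "What is your biggest issue with being able to take your medication"

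The survey has two uses. First, it selects subjects for Part 2. Section 6.2.3.1.1.2 describes the condition as "Reports non-adherent due to medication intolerance, defined by pre-determined criteria from Adherence Survey", and 6.2.4.2.1 and Appendix 7 give the same rule: a positive answer to question 3, 7 or 11, and more than 2 missed doses on question 8, 9 or 10. A current integrase regimen is also required (6.2.3.1.1.1). Second, it supplies the adherence outcome. Section 8.5.1.1 says that "employing Rasch analysis we will convert the data to a standardized range from 0 to 100". Section 8.6.1 uses the Rasch score for the Part 2 primary endpoint, with optimal adherence at 90 or above and a hypothesised minimum of 85% of subjects reaching it. No item is named as left out of the score.

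**The concern.** The Part 2 objective (3.2.1.1) concerns people whose suboptimal adherence is caused by side effects of an integrase regimen. The survey is the only instrument that establishes the cause, and every item that does so leaves the drug open. Someone who takes other long-term medicines may answer about those, and the change of wording on one sheet gives a careful reader some reason to think a difference is intended.

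Two things are at stake. A subject can be enrolled, and have ART switched under 6.2.4.1.1, for an intolerance that ART did not cause. And a subject who takes every dose of study drug, but forgets to pack or stops some other medicine, can give answers that count against ART adherence. No later analysis can recover which drug a respondent had in mind.

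**Working it through.** The protocol gives no figure on this point to reproduce. The check sets the items beside the rules that use them, then asks what an affected answer could do to the score.

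**Scope of each item against its use**

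| Items | Drug scope as printed | Use in the Part 2 screen |
|---|---|---|
| 1, 5 | HIV | none |
| 8, 9, 10 | HIV | missed-dose condition (any one) |
| 3, 7, 11 | not stated | side-effect condition (any one) |
| 4, 6 | not stated | none |

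So 3 of 3 side-effect routes are unqualified and 3 of 3 missed-dose routes are HIV-specific. Of the nine closed or numeric items (1 and 3 to 10), four are unqualified: 3, 4, 6 and 7.

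**Entry.** Take a patient on an integrase regimen who forgets four HIV doses a month and skips a non-HIV drug because it makes them ill. Question 10 is 4, above 2, so the missed-dose condition is met. Question 7 read as printed is Yes, so the side-effect condition is met. The screen is positive, and both answers are true. If question 7 named HIV medication the answer would be No; with questions 3 and 11 reworded likewise, the screen would be negative. A patient who misses 2 or fewer HIV doses on all three missed-dose items fails whatever the answer to question 7.

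The follow-up in question 7 asks which side effects, not which drug. Section 6.2.4.3.1 records current medications and medication history at screening, but no listed step requires the side effect to be traced to the HIV regimen.

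**Score.** No scoring key is given. The figures below rest on assumed keys and show only whether one affected Yes, on an otherwise perfect sheet, could cross 90.

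Raw shares:
- nine equally weighted items: 8/9 = 88.9, below the cut
- ten equally weighted items: 9/10 = 90.0, on the cut and so optimal under 8.6.1.2
- summed points, six yes/no items (6) plus question 8 (0 to 6), total 12: 11/12 = 91.7
- adding question 9 (0 to 7), total 19: 18/19 = 94.7
- adding question 10 (0 to 30), total 49: 48/49 = 98.0

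A Rasch score is not linear in the raw total, so a partial-credit conversion was also run. Yes/no items were placed at 0 logits and frequency-item thresholds centred at 0. Each raw total was converted to the logit at which the expected total equals it. The two extreme totals were moved inward by 0.3 or 0.5 points, and the logits were rescaled linearly to 0-100. One point below perfect gives:

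| Assumed key | Adjustment 0.3 | Adjustment 0.5 |
|---|---|---|
| 12 points, all thresholds equal | 79.7 | 85.8 |
| 12 points, thresholds 1.4 logits apart | 84.6 | 89.4 |
| 19 points, thresholds 1.4 logits apart | 88.0 | 92.1 |
| 19 points, thresholds 3 logits apart | 91.4 | 94.2 |

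Spacings of 1.4 and 3 logits both lie within the 1.4 to 5 that 8.5.2.1 accepts. The results fall on both sides of 90.

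**The case against.** The strongest reply is that context settles the meaning. The form is titled an ART survey, asks early on how long the patient has been on ART, and prints a list of HIV regimens beside the first items. Question 1 names HIV medications before any unqualified item appears. Question 11 directly follows two HIV-specific items, and the last option of question 8 itself speaks of the medication without a qualifier. The form is offered only to HIV-positive patients on ART. All of this stands and makes the HIV reading the likelier one. It does not make it the only one, since no instruction restricts the unqualified items, and nothing in the protocol shows how respondents read them.

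Second, a reader might infer that non-HIV drugs alone can decide entry. They cannot: an integrase regimen and more than 2 missed HIV doses are also needed. What remains is the narrower case worked above.

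Third, a reader might infer a definite downward bias in the primary result. The documents do not support that. Which items are scored, and how, is not stated, and no source gives the share of subjects who would answer about other drugs. Section 4.2.1.1 also states the endpoint as a change from baseline, where stable behaviour with other medicines would partly cancel. The 85% hypothesis in 8.6.1.2 concerns subjects reaching the cut, so that cancellation does not apply to it. Study-drug pill counts give a drug-specific comparison, but only as a secondary endpoint (4.2.2.7, 8.2.2.2.2).

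Last, naming HIV medication would still not identify the integrase component. That is correct and limits what the fix can claim.

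**Conclusion.** The inconsistency is plain on the form, and it falls on the items that define why a subject enters Part 2. A patient outside the population of 3.2.1.1 can truthfully screen positive, provided that HIV doses are also being missed for some other reason. This needs no assumption beyond the respondent taking the unqualified wording at face value.

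The effect on the score rests on one further assumption, that questions 3, 4, 6 and 7 enter the Rasch score. Section 8.5.1.1 implies this but does not say so. On that assumption an answer about a non-HIV drug can lower a score read as ART adherence, but whether it changes a subject's classification depends on the key. The number of subjects affected, at entry or at Week 16, cannot be estimated from the protocol. Priority is minor to moderate: a small ambiguity with no demonstrated effect on the result, but one that is cheap to remove beforehand and cannot be undone afterwards.

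**What to change.** In Appendix 1, reword questions 3, 4, 6, 7 and 11 so that each refers to the respondent's HIV medication, as questions 1, 5, 8, 9 and 10 already do. Use that version in Part 1 and at every Part 2 visit. If surveys have already been collected, record the form version with each one and report the primary result without questions 3, 4, 6, 7 and 11 as a sensitivity check. That check addresses the score only; it cannot show which subjects entered because of another drug.

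The cost is a few words on the site's own form with IRB approval (9.5.5), and two form versions if collection has begun. The sample size, visits and planned analysis stay as they are. The survey's psychometric properties are still to be assessed in Part 1 (8.2.1.2.1), so no validation described in the protocol is lost. The change narrows reported intolerance to HIV drugs; it does not by itself attribute it to the integrase component.
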